56 oral solution. By design, the study will be double-blinded insofar as neither investigators nor subjects will be notified of the
57 identity of the substances they are inhaling or swallowing. We anticipate blinding to scent may be challenging and the

58 study will include a post-study survey to ascertain the extent to which this blinding was achieved. Potential subjects are
59 those presenting to the SAMMC ED with symptoms of nausea and/or vomiting. For the purposes of this study, nausea is
60 defined as the subjective sensation associated with the urge to vomit, and vomiting is defined as the forceful expulsion of
61 gastric contents. Investigators will approach subjects at the time of initial triage and/or while in the waiting room. This will
62 mitigate interruptions in the subject's treatment, possible withdrawals from the control group, and lack of subject interest in
63 the study. Part of the screening process will entail solicitation of nausea on a VNRS scored from 0-10 with those patients
64 reporting scores of 3 or greater eligible for study. Informed consent will be obtained from each subject. Upon enrollment,
65 a study team member will record the patient's date of visit, FMP + sponsor social security number, and date of birth
66 (month, day, year) on the study key which will be maintained in a locked cabinet in the principal investigator's office.
67

68 Regarding blinding, subjects will be informed they will be nasally inhaling one of two common medical preparation pads
69 saturated with different ingredients and taking orally one of two common oral solution substances. Subjects will be
70 allocated to one of three arms: (1) inhaled isopropyl alcohol plus oral ondansetron; (2) inhaled isopropyl alcohol plus oral
71 placebo; (3) inhaled placebo plus oral ondansetron. No subject will receive both inhaled and oral placebo; all subjects will
72 be allocated to at least one therapeutic intervention for nausea. Both investigators and study subjects will be blinded to
73 subject allocation. Randomization will be performed prior to study start with a computer-generated assignment (simple
74 randomization sequence) by an individual not otherwise involved in the study. A copy of the randomization key will be in a
75 sealed envelope and placed in the study file box along with study packets as to be readily available in the ED in case un-

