73 study investigators and secured daily in a locked cabinet, along with locked study file box, in the EM APD-R office.

74
75

Assessment	Visit / Follow Up (F/U) Interval Times					
	Initial Presentation	0 min (patient drinks oral solution and starts inhalations)	q10 min until 30 min	1 hour	Hourly until 5 hours	Disposition decision made by patient's attending physician
Study period/interval						
Screening	x					
Informed Consent, discuss Plan, etc.	x					
Allocation according to pre-generated simple randomization sequence	x					
Demographics, History of Present Illness	x					
Medication use	x					
Preparation pad provided		x				
Additional preparation pad offered if needed (up to 10)			x	x	x	
Oral solution provided		x				
Provider contacted for consideration of rescue anti-emetic if vomiting or if subject requests			x	x	x	
Nausea Vomiting VAS		x	x	x	x	x
Episodes of Vomiting		x	x	x	x	x
Pain VAS		x	x	x	x	x
Use of Antiemetic Medication		x	x	x	x	x
Type/Doses of fluids/medications		x	x	x	x	x
Clinical impression						x
Overall Satisfaction VAS						x
Pt perception of pad contents						x
Pt perception of oral solution contents						x
Provider perception of pad contents						x
Provider perception of oral solution contents						x
Investigator perception of pad contents						x
Investigator perception of oral solution contents						x
Summary of adverse events						x

76
77
78
79
30
31

This study concludes at the time of disposition and patient satisfaction will be solicited regardless of outcome.

7.3.1 Collection of Human Biological Specimens. Not applicable.

7.3.1.1 Laboratory evaluations and special precautions. Not applicable.

32
33 **7.3.1.2 Specimen storage.** Not applicable.
34

35 **7.3.2 Data Collection.**

- 36 -Times of subject arrival to ED, bed arrival, study medication receipt (gathered prospectively from order sheet or Essentris)
37 -Patient initial nausea as measured by screening VNRS (0-10): self-reported by the subject.
38 -Demographics: Age in years, sex, FMP/SSN, DOB will be recorded on the study key. Age in years and sex will also be
39 reported on the case report form (CRF). This information will be obtained from the patient's ED medical record labels.
40 -The patient's estimated height, weight, race, smoking history, alcohol use will be recorded on the CRF as self-reported by the
41 patient.
42 -History of Present Illness- Nausea and/or vomiting symptoms of timing, duration, severity, provocation and palliation along

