43 with any other symptoms (i.e. pain) will be recorded on the CRF. This information will be self-reported by the subject.
44 -Pertinent Personal Medical/Surgical History will be recorded on the CRF. This information will be self-reported by the
45 subject.
46 -Current medications, supplements being taken and any allergies will be recorded on the CRF.
47 -Level of nausea, episodes of vomiting, pain level, adverse events, use of antiemetic medication at the 0, 10, 20, 30, and 60
48 minutes, then hourly up to 5 hours and finally at the time of patient disposition will be recorded on the CRF. Satisfaction level
49 will be recorded at study conclusion (time of patient disposition) on a VAS. This information will be self-reported by the
50 subject.
51 -Numbers of episodes of vomiting (discrete episodes separated by 120 seconds) will be recorded on the CRF as reported by
52 the patient or the patient's treating nurse.
53 -Time and doses for all drugs and fluids administered in the ED will be recorded on the CRF.
54 -Clinical impression at the time of patient disposition decision will be recorded on the CRF.
55 -Time of patient disposition decision made by attending physician will be recorded on the CRF.
56 -Any adverse events will be recorded on the CRF.
57 -Patient, provider, and study investigator perceptions of pad and oral solution contents will be recorded on the CRF.

58
59 **7.3.3. Human Biological Specimens/Tissue/Data Banking.** Not applicable.
60

61 **7.4 Statistical Consideration**

62
63 **7.4.1 Sample Size Estimation.**

64 **We expect the standard deviation of the change in baseline to 30 minute VAS scores to be approximately 28.7.¹⁷ We**
65 **define a clinically significant difference as 20 mm on the VAS.¹⁸ Given alpha = 0.025 (reflecting a Bonferonni**
66 **correction for testing of two hypotheses) and beta = 0.2 with two-tailed testing, we estimate we will require 40**
67 **patients per arm.**
68

Estimate Required Sample Size	120
Estimate Participant Drop Out / Withdrawal	60
Total Enrollment Requirement	180

69

Enrollment at Each Site	
SAMMC	180

70
71 **7.4.2 Primary (i.e., primary outcome variables) and secondary endpoints.** Primary outcome is nausea VAS measurement
72 at 30 minutes. Secondary outcomes include nausea VAS measurement at study disposition (the time at which the patient
73 leaves the ED), receipt of rescue anti-emetics, time to disposition, and patient satisfaction.
74

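### Sample size is set per arm, but simple randomisation leaves arm sizes to chance; a restricted list is a cheap, minor improvement

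*Combined protocol and SAP*

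**What the plan says.** Section 6 (Research Design) sets the method: "Randomization will be performed prior to study start with a computer-generated assignment (simple", and the parenthesis goes on to call it a randomisation sequence. The table in Section 7.3 repeats it: "Allocation according to pre-generated simple randomization sequence". Neither place mentions blocks, stratification, a target ratio or a check on arm totals. The list is made by someone not otherwise involved in the study, and the packets and oral doses are prepared from it.

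Section 7.4.1 states the size per arm: "correction for testing of two hypotheses) and beta = 0.2 with two-tailed testing, we estimate we will require 40" patients per arm. That makes 120, to which 60 are added for drop-out and withdrawal, giving 180 enrolled.

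Two inputs are not written down. The allocation ratio is inferred as 1:1:1 from three arms of 40. Two hypotheses are counted for the Bonferroni correction, but Section 6 spells out only one: inhaled alcohol plus oral placebo against inhaled saline plus oral ondansetron.

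**The concern.** A requirement stated per arm is paired with an allocation method that controls only the total. The precision of a two-arm comparison depends on 1/n1 + 1/n2, so a short arm weakens every comparison it enters. The sponsor draws one list, so an average over possible lists gives no protection against a poor draw. Simple allocation also leaves balance over calendar time to chance, in a convenience sample recruited within a two-year project.

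What is at stake is modest: some precision, and a higher chance of an avoidably weak comparison if losses turn out heavy. The validity of the t test is not affected.

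**Working it through.** **Inputs.** From Section 7.4.1: difference 20 mm, SD 28.7 mm, two-sided alpha 0.025 per comparison, power 0.80, 120 evaluable, 60 losses, 180 enrolled. Assumed: 1:1:1 allocation, loss at random and unrelated to arm, and two comparisons sharing one arm.

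**The plan's figure.** n per arm = 2 × [28.7 × (2.241 + 0.842) / 20]² = 39.15, rounded up to 40. This reproduces the plan. Power at 40 v 40 is 80.9% by the normal approximation and 79.5% by the noncentral t. Enrolment also reproduces: 120 / (1 − 1/3) = 180.

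**Spread at randomisation.** Under simple allocation each arm is binomial(180, 1/3), with mean 60 and SD √(180 × 1/3 × 2/3) = 6.3. In simulation, the largest and smallest arms differ by 13 on average, and by 15 or more in 38% of lists.

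**After loss.** I drew 1,000,000 trials per row: arm sizes from a multinomial (simple) or set at 60/60/60 (fixed), then binomial retention in each arm. Power is from the noncentral t. Each cell is simple v fixed.

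| Random loss | Mean smallest arm | P(some arm below 40) | Mean power per comparison | P(at least one comparison below 75% power) |
|---|---|---|---|---|
| 0% | 53.5 v 60 | 0.1% v 0% | 93.4% v 93.8% | 0% v 0% |
| 20% | 42.2 v 45.4 | 22% v 1.4% | 86.4% v 86.8% | 0.1% v 0% |
| 25% | 39.4 v 42.1 | 48% v 15% | 83.8% v 84.3% | 1.5% v 0.1% |
| 33.3% | 34.7 v 36.9 | 93% v 82% | 78.7% v 79.2% | 29% v 14% |

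**How much is due to the list.** At one-third loss the smallest arm averages 40 − 34.7 = 5.3 below target under simple allocation. Under exact 60/60/60 it still averages 40 − 36.9 = 3.1 below. So 2.2 of the 5.3 go away with a restricted list, and the rest comes from uneven loss.

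**Why mean power hardly moves.** When one arm is short the others are larger. A comparison of 35 v 43 has 77.9% power, against 79.5% at 40 v 40. At one-third loss the weaker of the two comparisons averages 76.6% under simple and 78.0% under fixed allocation.

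**The case against.** Simple randomisation gives valid inference and is the least predictable method. That counts here, because Section 6 expects blinding to scent to be difficult, and an investigator who guesses pad contents could use a block pattern to anticipate the next packet. The total of 180 carries a large margin. The primary outcome is read at 30 minutes within one emergency visit, and Section 10.0 keeps data collected before withdrawal unless the patient asks for destruction, so losing a full third is far from certain. The 29% v 14% contrast also depends on a 75% cut-off placed just below the planned power; at a 70% cut-off it is about 4% v 1%.

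Most of this stands. It removes any claim that planned power is lost, and it makes the choice of restricted method matter. It does not show that unrestricted allocation is better here. Predictability is a problem mainly with small blocks of fixed, known size, and much less with concealed varying blocks or one permutation of the whole list. The restricted list also gives a larger smallest arm at every loss rate examined. At 20% to 25% loss, where dropout alone seldom takes an arm below 40, the allocation method accounts for most of that risk.

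**Conclusion.** The point holds as a minor, optional improvement. The plan sets its size per arm and uses an allocation method that does not control arm size. Depending on loss, this costs on average about 2 to 6.5 patients in the smallest arm and about half a point or less of mean power. Only near the full one-third loss does it add appreciably to the chance of a weak comparison.

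A reader might infer that an arm of about 35 is to be expected, or that the trial is underpowered. The documents support neither. An arm of about 35 is the average smallest arm only if the whole allowance of 60 is used; at 20% loss the average is 42.2. Even exact 60/60/60 allocation leaves some arm below 40 in 82% of trials at full loss. Nor can it be said that exactly one of two comparisons would suffer: if the shared arm is the smallest, both would, and the second comparison is not named.

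The figures rest on the assumed 1:1:1 ratio, random loss and shared arm. The documents give no expected loss other than the allowance, hence the range.

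**What to change.** In Section 6 and the Section 7.3 table, replace the simple sequence with a restricted 1:1:1 list, state the ratio, and have it prepared before study start by the independent individual already named.

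- **Preferred:** permuted blocks of randomly varying size, with sizes not disclosed to investigators. These also hold balance over calendar time, and if recruitment stops early.
- **Alternative:** one random permutation of 60/60/60 labels over the 180 packets. It is less predictable, but it fixes the totals only if all packets are used and does little for calendar balance.

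If the list already exists, the preparer can check its arm totals without telling the investigators.

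The cost is a different list command before packets and oral doses are prepared. The downside is slight predictability, which matters somewhat given the expected difficulty with scent blinding and is the reason to keep block sizes varying and concealed.

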35 blinded studies examined time to 50% reduction in nausea as measured on a verbal numerical rating scale (VNRS), 0-11,
36 finding isopropyl alcohol achieved this more rapidly than conventional anti-emetics such as promethazine and
37 ondansetron (times ranging 6.5-15.0 minutes).⁵⁻⁷ A fourth study was single-blinded and reported absolute VNRS (0-11)
38 for isopropyl alcohol versus usual anti-emetics (not otherwise specified). This study found scores decreased from a mean
39 of 5.7 pre-inhalation to 2.7 post-inhalation though this was not significantly better than the usual care arm.⁸ A fifth study
40 compared inhaled isopropyl alcohol plus ondansetron versus ondansetron alone concluding no significant differences in
41 nausea as measured on a 0-11 VNRS.⁹ An additional three studies compared inhaled isopropyl alcohol to inhaled
42 placebo, all of which concluding that isopropyl alcohol resulted in superior nausea relief.¹⁰⁻¹² Finally, a randomized trial
43 with three arms including inhaled peppermint, inhaled isopropyl alcohol, and inhaled placebo found no difference in
44 nausea scores as measured by a visual analogue scale (VAS).¹³ In total, the Cochrane review article broadly concluded
45 efficacy for isopropyl alcohol in treating post-operative nausea and vomiting. These studies were limited in that none were
46 performed in an outpatient or pre-hospital setting. More recently, a randomized controlled trial at San Antonio Military
47 Medical Center (SAMMC) demonstrated efficacy at 10 minutes among ED patients with nausea or vomiting.¹ Of note,
48 although traditional anti-emetics (e.g., ondansetron, promethazine, metoclopramide) have demonstrated efficacy in
49 specific patient populations such as cancer patients receiving chemotherapy,¹⁴ multiple studies have found these agents
50 are no better than placebo in treating nausea among undifferentiated ED patients.¹⁵⁻¹⁷ Despite the absence of efficacy
51 data, these agents are frequently used in the treatment of nausea among ED patients. Our objective is to compare the
52 efficacy of inhaled isopropyl alcohol to ondansetron in treating nausea among undifferentiated patients.

53
54 **6. RESEARCH DESIGN** This study is a prospective randomized controlled trial. We will test the hypothesis that nasally-
55 inhaled ISO plus oral placebo has greater anti-emetic efficacy compared to nasally-inhaled saline plus oral ondansetron

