75 **7.4.3 Data analysis.** In this study, the primary outcome will be evaluated using a two-tailed independent sample student t test.
76 The primary outcome will further be evaluated using a multiple regression model. For secondary outcomes, scale data will be
77 compared using a two-tailed independent sample student t test while categorical data will be compared using a chi-squared
78 test.
79

80 **7.7 Confidentiality.**

31 Protection of Data. Subjects will be assigned a study number upon enrollment in order to facilitate subsequent removal of
32 identifiers upon completion of data analysis. The study number will be recorded on the data collection form and on a study
33 key, which links the study number with the subject's name, FMP, SSN, and DOB. Otherwise patients will be de-identified by
34 eliminating names and collecting only demographic (with ages greater than 89 categorized as "greater than 89"), general
35 description of chief complaint, personal medical, surgical, and medication history; and any other information specific to
36 inclusion and exclusion criteria. The case report forms, signed consent forms, and signed HIPAA authorizations will be stored
37 in a locked cabinet only accessible to the study investigators within the secure EM APD-R office.

38
39 **7.7.1 Certificate of Confidentiality.** N/A.

40 41 **8.0 RISKS/BENEFITS ASSESSMENT**

42
43 **8.1 Risks.** There is a risk to the subjects related to loss of confidentiality. However, this risk is minimized by using a
44 unique study code while collecting study data and limiting access to subject records to the study team. Since all patients
45 will be receiving treatment for nausea (either inhaled isopropyl alcohol, oral ondansetron, or both), we believe the risks of
46 delay in treatment or symptom relief are minimal. Nevertheless, if the treatment to which subjects are allocated is not
47 effective in treating their symptoms, they may experience a delay in rescue therapy and so a delay in symptom relief. We
48 seek to minimize this risk by permitting, subjects to request an antiemetic at any time and to withdraw from the study at
49 any time.

50
51 Additionally, there may be an extremely rare incident of a subject that may have a sensitivity to inhaling ISO. The
52 exclusion criteria were defined to minimize the risks of such reactions by excluding patients recently exposed to
53 medications such as cefoperazone, disulfiram, or metronidazole.

54

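### The Bonferroni split in Section 7.4.1 is valid, but Holm on the same two contrasts keeps the 5% familywise bound, never rejects less and needs no extra patients

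*Combined protocol and SAP*

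**What the plan says.** Section 7.4.1 allows for two hypotheses by setting alpha at 0.025 for each, with the "correction for testing of two hypotheses) and beta = 0.2 with two-tailed testing". It takes 20 mm as the clinically meaningful difference, expects the "standard deviation of the change in baseline to 30 minute VAS scores to be approximately 28.7", and arrives at 40 patients per arm, 120 in all. Adding 60 for dropout gives a "Total Enrollment Requirement" of 180.

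Section 7.4.3 says that "the primary outcome will be evaluated using a two-tailed independent sample student t test" and adds: "The primary outcome will further be evaluated using a multiple regression model". It gives no alpha, no multiplicity rule and no list of contrasts, and does not say which of the two analyses decides.

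Only one of the two hypotheses is put into words. Section 6 states that "inhaled ISO plus oral placebo has greater anti-emetic efficacy compared to nasally-inhaled saline plus oral ondansetron", which is arm 2 against arm 3. The second is not named; it could be arm 1 (ISO plus ondansetron) against arm 3, or arm 1 against arm 2.

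**The concern.** Plain Bonferroni tests the second contrast at 0.025 even after the first has been won. Holm tests the smaller p-value at 0.025, exactly as Bonferroni does, and only if that succeeds tests the other at 0.05. Both procedures bound the familywise error at 5% under any dependence between the tests, including that from a shared arm. Staying with Bonferroni therefore gives up power without buying tighter familywise control.

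What is at stake is mainly the chance of establishing both contrasts from the same patients. How much the Section 6 hypothesis gains depends on the second effect, and Section 5 gives reason to think that effect may be small. It cites a study that "compared inhaled isopropyl alcohol plus ondansetron versus ondansetron alone concluding no significant differences in" nausea, which bears on arm 1 v arm 3. It also reports that conventional anti-emetics "are no better than placebo in treating nausea among undifferentiated ED patients", which bears on arm 1 v arm 2.

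**Working it through.** **Inputs.** From Section 7.4.1: difference 20 mm, SD 28.7 mm, alpha 0.025 two-sided, power 80%, 40 per arm; 180 enrolled, so 60 per arm if nobody drops out. From Section 7.4.3: two-sample t test. Assumed: the second contrast and its effect, normal data and equal arms. The SD is stated for the change score but is applied here to the 30-minute score, whose SD the plan does not give.

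**The plan's own figure.** n per arm = 2 × (SD/difference)² × (z₀.₉₈₇₅ + z₀.₈₀)² = 2 × (28.7/20)² × (2.241 + 0.842)² = 39.15, rounded up to 40. Exact t power for 20 mm:

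| n per arm | alpha 0.025 | alpha 0.05 |
|---|---|---|
| 40 | 79.5% | 86.8% |
| 60 | 93.8% | 96.6% |

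The 0.05 column is the ceiling for one contrast under Holm; the 0.025 column is the floor.

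**Holm against Bonferroni.** Figures are from 1,000,000 simulated three-arm trials per scenario with pooled t tests. H1 is arm 2 v arm 3 with a true effect of 20 mm.

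H2 = arm 1 v arm 3:

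| n per arm | H2 effect | H1 power, Bonferroni | H1 power, Holm |
|---|---|---|---|
| 40 | 0 mm | 79.5% | 79.7% |
| 40 | 10 mm | 79.5% | 80.2% |
| 40 | 20 mm | 79.5% | 84.4% |
| 40 | 30 mm | 79.5% | 86.7% |
| 60 | 0 mm | 93.8% | 93.9% |
| 60 | 10 mm | 93.8% | 94.0% |
| 60 | 20 mm | 93.8% | 96.0% |
| 60 | 30 mm | 93.8% | 96.6% |

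Both contrasts won at 20/20 mm: 68.1% to 77.6% with 40 per arm, 89.2% to 93.7% with 60. At 20/10 mm and 40 per arm: about 23% to 32%.

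H2 = arm 1 v arm 2, 40 per arm: H1 power under Holm is 79.7% if the arms are equal, 82.3% or 86.3% if arm 1 is better by 10 or 20 mm, and 80.2% or 84.3% if it is worse by 10 or 20 mm. Both won goes from 60% to 74% if arm 1 is better by 20 mm, and from 68% to 78% if it is worse by 20 mm.

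**Consistency check at 20/20 mm, 40 per arm, arm 1 v arm 3.** Under Bonferroni, at least one win = 79.5 + 79.5 − 68.1 = 90.9%, which agrees with the simulated 91.0%. Holm cannot change this, because its first step is Bonferroni's. The extra 77.6 − 68.1 = 9.5 points in winning both are second-step wins; by symmetry each contrast gains half, about 4.8 points, so 79.5% becomes about 84.3%. With 60 per arm, at least one win is 98% under both procedures.

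**Error rates.** Under the global null the familywise error is about 4.7% for both procedures. If one contrast is null and the other effect is 20 mm, the null contrast is rejected in 2.5% of trials with Bonferroni, and with Holm in 4.3% (40 per arm) or 4.6% (60 per arm). With a very large other effect the Holm rate is 4.99%, still within 5%.

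**Sensitivity to the SD (assumed 25 or 32 mm; 20/20 mm, 40 per arm).** SD 25: H1 89.9% to 93.1%, both won 83% to 90%. SD 32: H1 69.4% to 74.9%, both won 55% to 66%.

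**Fixed sequence as an alternative.** Testing H1 first at 0.05 gives it 86.8% power at 40 per arm whatever H2 is. But H2 cannot be won if H1 fails: at 20/20 mm the chance of at least one win falls from 91% to 87%, and arm 1 v arm 3 power at a 30 mm effect falls from 99% to 87%.

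**The case against.** The strongest reply is that this is a preference. Bonferroni is pre-specified and valid, no figure in the plan is wrong, and winning both contrasts is nowhere a success criterion. Sections 3 and 6 ask one question, ISO against ondansetron, and on it Holm adds only 0.2 to 0.7 points if the second effect is 0 to 10 mm. This stands, and it is why the point is an improvement rather than an error.

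Next, 68% to 78% depends on a contrast the plan never names. If both ISO arms are 20 mm better than arm 3 but the second contrast is arm 1 v arm 2, that contrast is null and H1 gains almost nothing. This is true as a limit on the size. It does not touch the principle: whichever contrast is meant, Holm never rejects less.

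Third, the extra wins are modest differences. The standard error is 28.7 × √(2/40) = 6.42 mm, so p between 0.025 and 0.05 means an observed difference between 1.991 × 6.42 = 12.8 mm and 2.285 × 6.42 = 14.7 mm (10.4 to 11.9 mm with 60 per arm), below the plan's 20 mm. The matching 97.5% interval includes zero. Bonferroni's simple simultaneous intervals are a real merit. But a Bonferroni win can also fall anywhere from 14.7 mm upwards, so falling short of 20 mm is not peculiar to Holm.

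Last, naming the contrasts matters under either procedure: three arms allow three pairwise tests, and all three at 0.025 would give about 6.4% familywise error under the global null. That is right, and Holm does not cure it. It is a reason to write both into the same sentence. Simple randomisation will make arm sizes unequal, but that affects both procedures alike.

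**Conclusion.** The concern holds as a cheap improvement. The two-test Bonferroni split is sound and 40 per arm reproduces, but Holm does at least as well on every power figure above and keeps the 5% bound. At 40 per arm the gain in winning both is about 10 points when both effects are 20 mm and arm 3 is shared. For the Section 6 hypothesis, with arm 1 v arm 3 as the second contrast, it runs from 0.2 points (second effect 0 mm) to about 7 (30 mm). If all 180 are evaluable, the gains shrink to about 4.5 points for both and 0.1 to 2.8 for H1. The chance of at least one win does not move. These sizes rest on an assumed second contrast and effect, and on an SD of 28.7 mm carried over from the change score. That Holm never rejects less and keeps the bound rests on none of these.

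**What to change.** In Sections 7.4.1 and 7.4.3, replace Bonferroni with Holm at an overall two-sided 0.05 on the two primary contrasts of the 30-minute nausea VAS: compare the smaller p-value with 0.025 and, only if it is significant, the other with 0.05. In the same place, before unblinding, record H1 as ISO plus oral placebo v saline plus ondansetron, and name the second contrast the sponsor already intends. State that the t test decides and the multiple regression is supportive. Keep 0.025 as the planning alpha, since it is Holm's first step; 40 per arm need not change.

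The cost is two or three sentences, with no extra patients or data. There are two downsides to accept openly:

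- A null contrast beside a real 20 mm effect is rejected in 4.3% to 4.6% of trials instead of 2.5%.
- A second-step win with p between 0.025 and 0.05 has a 97.5% interval that includes zero. At 20/20 mm this occurs in 9.5% of trials with 40 per arm and 4.5% with 60, and the report should say so when it happens.

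A fixed sequence is defensible if H1 is all that matters, at the cost in at-least-one and second-contrast power shown above.
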